7.2.5.4 Data Collection Period

This study involving both prospective and retrospective data collection.

The retrospective data collection period will be defined as date of posaconazole injection and tablet formulations has been approved by NMPA for the treatment of IA in adult patients (29 Mar 2022) until the start of recruitment period (Oct 2023 as planned).

The prospective data collection period will be defined as the start of recruitment period (Oct 2023 as planned) until the the planned patients last visit date of the study (Jan 2025).

7.2.5.5 Patient Index Date and Specific Treatment Assessment Durations

Patient index date is defined as the date of the first treatment of posaconazole injection and/or tablet formulations.

	30
PRODUCT: MK5592	PROTOCOL/AMENDMENT VERSION NO.: 2
REVOPS ID NO: NIS102646	CORE DRC APPROVAL DATE: 18-SEP-2024
EPIDEMIOLOGY NO.(PE STUDIES ONLY): EP08047.004	

Specific treatment assessment duration for different outcomes are summarized as follows:

- Assessment for all-cause mortality for IA will occur at Day 42. Treatment may continue beyond Day 42.
- Assessment for overall response will occur at the end of treatment (for both first line and salvage treatment). Patients may continue treatment beyond 12 weeks (84 days) however assessment for response to therapy will occur at 84 days for such patients. For patients who receive less than 12 weeks of treatment, assessment will occur at the end of posaconazole treatment.

7.3 Variables

7.3.1 Exposure

The study exposure of interest is posaconazole injection and/or tablet formulations treatment administered in a non-interventional setting. The study will include patients who received posaconazole injection and/or tablet formulations treatment in routine clinical practice.

7.3.2 Outcomes

Health outcomes is definited as clinical events or outcomes which may be represented as diagnoses, treatment or procedures (examples include syncope, disease progression or hypoglycemia collected as study endpoints)

Any herein described health outcomes, collected per the protocol, will be summarized as part of any interim analysis (if required) and in the final study report in addition to being reported in real-time as individual AE/s if the criteria in section 7 are met. Refer to section 9 for AE reporting requirements and procedures.

7.3.2.1 Primary Outcomes

The primary outcome is all-cause death among proven, probable, possible IA patients who received at least 7 days of posaconazole injection and/or tablet formulations treatment through Day 42.

Death is defined as a patient with death is recorded in the medical history or death certificate can be provided through Day 42 or within Day 42. (Data cources see 7.4)

Patients with missing or 'unable to determine' dead or alive status through Day 42 will be excluded.

PRODUCT: MK5592	PROTOCOL/AMENDMENT VERSION NO.: 2
REVOPS ID NO: NIS102646	CORE DRC APPROVAL DATE: 18-SEP-2024
EPIDEMIOLOGY NO.(PE STUDIES ONLY): EP08047.004	

Secondary Outcomes 7.3.2.2

7.3.2.2.1 **Clinical response**

The clinical response of proven, probable, possible IA patients who received posaconazole injection and/or tablet formulations treatment as the first line or salvage treatment at the end of posaconazole treatment.

Clinical responses will be defined by using the 2017 Chinese guidelines for the diagnosis and treatment of invasive fungal disease in patients with hematological disorders and cancers (the fifth version) (Table 1) or by the investigator⁷(s).

⁷Considering the low compliance with guidelines in real-world clinical practice, it is possible that there may be insufficient information from medical record to support the definition of clinical response according to the guideline (Table 1). Therefore, investigator's professional judgment could be used to define the clinical response. The subgroup analysis by the methods of clinical response definition (guideline vs. investigator's professional judgment) will be conducted depending on data availability. (see 7.7.2.1)

See Table 1 for the definitions for clinical response from the 2017 Chinese guidelines for the diagnosis and treatment of invasive fungal disease in patients with hematological disorders and cancers (the fifth version). The Chinese guidelines are consistent with the 2008 EORTC/MSG guidelines.

Table 1 Clinical Response Definitions from the 2017 Chinese guidelines for the diagisnos and treatment of invasive fungal disease in patients with hematological disorders and cancers (the fifth version).

Outcome, Response	Criteria
Success	
Complete response	Survival within the prespecified period of observation, resolution of all attributable symptoms and signs of disease [Aspergillus spp], resolution of radiological lesion(s), and documented clearance of infected sites that are accessible to repeated sampling.
Partial response	Survival within the prespecified period of observation, improvement in attributable symptoms and signs of disease [Aspergillus spp], improvement of radiological lesion(s) ^a , and evidence of clearance of infected sites that are accessible to repeated sampling.
	In the case of radiological stabilization ^b , resolution of all attributable symptoms and signs of fungal disease; or where biopsy of an infected site shows no evidence of hyphae; or where culture is negative.

08R565

Confidential

	32
PRODUCT: MK5592	PROTOCOL/AMENDMENT VERSION NO.: 2
REVOPS ID NO: NIS102646	CORE DRC APPROVAL DATE: 18-SEP-2024
EPIDEMIOLOGY NO.(PE STUDIES ONLY): EP08047.004	

Outcome, Response	Criteria
Failure	
Stable response	Survival within the prespecified period of observation and minor or no improvement in fungal disease; or persistent isolation of Aspergillus spp or histological present in infected sites.
Progression of fungal disease	Worsening of clinical symptoms and signs of disease [Aspergillus spp] plus new sites of disease or radiological worsening; or persistent isolation of Aspergillus spp from infected sites.
Death	All-cause death during the prespecified period of evaluation, regardless of attribution.

^a improvement of radiological lesions is defined as at least 25% reduction in diameter of radiological lesion. ^b radiological stabilization is defined as 0%-25% reduction in the diameter of the lesion.

Link: http://pubmed.ncbi.nlm.nih.gov/28592049/

Assessment for clinical response will occur at the end of treatment.

• For first line treatment of IA:

The duration of treatment range from 42 days to 84 days. Patients may continue therapy beyond 12 weeks however clinical response will be assessed at 12 weeks (84 days) for such patients).

• For salvage treatment of IA:

The duration of treatment range from 7 days to 84 days. Patients may continue therapy beyond 12 weeks however clinical response will be assessed at 12 weeks (84 days) for such patients).

Missing or 'unable to determine' treatment responses at assessment timepoint will be excluded.

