7.2.2 Inclusion/Exclusion criteria for subjects receiving first line treatment

Inclusion criteria for subjects receiving first line treatment of IA:

- Chinese and resident in China;
- At least 18 years of age on the day of initiating posaconazole treatment;
- Diagnosed with proven, probable, possible IA per EORTC/MSGERC 2020 or 2021 EORTC/MSGERC-ICU criteria;
- Has received less than 7 days of other antifungal therapy with activity against aspergillosis (amphotericin, voriconazole, isavuconazole, or itraconazole) for treatment of the current episode of IA.

Exclusion criteria for subjects receiving first line treatment of IA:

- Unable to provide written informed consent if Ethics review committee (ERC) requires;
- Participating in any interventional clinical trial;
- Pregnancy or breast feeding during the treatment with posaconazole;
- Prior enrollment in current study (each subject may only be enrolled once);
- History or known aspergillus infection with a strain that is azole-resistance;
- Known or history of efficacy failure of posaconazole to treat a prior or current episode of IA.

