7.4 Data Sources

Relevant patient-level information will be collected from multiple information systems, including EMR,paper medical records, Hospital Information System (HIS), Laboratory Information System (LIS), and routine patient management material from clinicians in selected hospitals. Medical records from other hospitals can be collected as needed The databases contain both inpatient and outpatient data.

For patient with retrospective data collection missing with dead or alive status in medical record, a follow up to confirm the dead or alive status through day 42 is required. Death certificate information or the follow-up contact/report/record by investigator would be the data sources.

All data will be collected with the use of a standardized case report form.

	36
PRODUCT: MK5592	PROTOCOL/AMENDMENT VERSION NO.: 2
REVOPS ID NO: NIS102646	CORE DRC APPROVAL DATE: 18-SEP-2024
EPIDEMIOLOGY NO.(PE STUDIES ONLY): EP08047.004	

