7.4.1 Study Procedures

This study administered in a non-interventional setting. The study protocol will be submitted for approval by the institutional review board (IRB)/ethics review committee (ERC). Figure 2 shows the procedures of eligible patients enrollment.

	37
PRODUCT: MK5592	PROTOCOL/AMENDMENT VERSION NO.: 2
REVOPS ID NO: NIS102646	CORE DRC APPROVAL DATE: 18-SEP-2024
EPIDEMIOLOGY NO.(PE STUDIES ONLY): EP08047.004	

Given that the study design involves prospective and retrospective data collection, the participating practitioner will obtain informed consent from patients included in prosepective data collection and submit the study to the IRB/ERC to let IRB/ERC determine whether the patients including in retrospective data collection qualifies to waive for informed consent. While doing retrospective data collection, if a follow up is need for patients to collect dead or alive status through Day 42, the informed consent should be obtained.

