7.8 Data Analysis

A descriptive analysis of the distribution of values abstracted for each variable will be provided. For the continuous variables we are interested, the values of mean/median, standard deviation (SD), min/max, interquartile range (IQR, including the first quartile [Q1] and third quartile [Q3]) will be calculated; the frequency and percentages will be calculated for these categorical variables. All analyses will be carried out using all available data. A participant with missing data on one variable will be used only in calculations that do not involve that variable.

	39
PRODUCT: MK5592	PROTOCOL/AMENDMENT VERSION NO.: 2
REVOPS ID NO: NIS102646	CORE DRC APPROVAL DATE: 18-SEP-2024
EPIDEMIOLOGY NO.(PE STUDIES ONLY): EP08047.004	

All analyses will use SAS (SAS Institute Inc., Cary, North Carolina). Detailed statistical analysis plan (SAP) and corresponding mock-up tables/figures/listings will be described separately prior to the commencement of any analyses.

All analysis detailed will be described in a separate "Statistical Analysis Plan". Key points are listed below.

7.8.1 **Primary Objective**

The primary objective is to assess the all-cause mortality of using posaconazole for proven, probable, possible IA patients. The all-cause mortality will be calculated with 95% CI.

Total all-cause mortality=number of total IA patients who die through Day 42/number of all IA patients (proven, probable, possible) included in the study with dead or alive status reported x 100%.

All-cause mortality by treatment line=number of IA patients by treatment line who die through Day 42/number of IA patients by treatment line (proven, probable, possible) included in the study with dead or alive status reported x 100%.

The analysis will be stratified by method of data collection: prospective vs. retrospective.

The following subgroupanalysis may be conducted depending on data availability:

- 1. Treatment duration (e.g. group by median treatment duration, etc);
- 2. Patients who only receive Posaconazole injection vs patients who receive Posaconazole injection then Posaconazole tablet;
- 3. Risk factors for mortality and poor outcome (Allogeneic hematopoietic stem cell transplant (HSCT); Relapsed leukemia, undergoing salvage chemotherapy; Liver transplant recipients)
- 4. IA at sites: Pulmonary IA vs others (sinus/upper respiratory involvement or disseminated disease to other organs).

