7.10 Limitations of the Research Methods

As this is an observational study, potential bias cannot be ruled out. Data collection will reflect routine clinical practice rather than mandatory assessments at prespecified time points, which may have an impact on the amount of data available and its interpretation. Potential sources of bias and limitations as well as strategies to minimize these are discussed further below.

First, cases from the potential leading site or potential sub sites may be sicker as these potential sites are the top-level hospitals in China. Patient with sicker situation in China

PRODUCT: MK5592	PROTOCOL/AMENDMENT VERSION NO.: 2
REVOPS ID NO: NIS102646	CORE DRC APPROVAL DATE: 18-SEP-2024
EPIDEMIOLOGY NO.(PE STUDIES ONLY): EP08047.004	

prefer top-level hospitals. Sicker cases will lead to lower ORR and higher ACM which may not reflect the real value of posaconazole. (Admission rate bias) To mitigate this bais, the following action will be implemented. The study design to assess the study outcomes (see 7.3.2) by different treatment lines (first line and salvage treatment) to differentiate patients' disease conditions. Patient characteristics by treatment line are also described as secondary endpoint.

Second, survivor cases from retrospective data collection are easier to be reached to sign the ICF in the recruitment period, at the same time, cases from retrospective data collection or prospective data collection may be lost to follow-up without clear alive or dead status or response data. These situations will lead to underestimate or overestimate the ACM/ORR. (Immortal time bias/ No-respondent bias/Survivor bias) To mitigate this bias, study design to contact not only the case himself/herself from retrospective data collection, but also their relatives to follow up with missing dead or alive status. And cases from prospective data collection will be closed monitor to make sure the alive or dead status and response data are recorded.

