8.1 Informed Consent

For retrospective data collection, the study will be submitted to the IRB/ERC to let IRB/ERC determine whether the study qualifies for the waiver of informed consent. In the situation where informed consent could not be waived, consent must be documented by the subject's dated signature or by the subject's legally acceptable representative's dated signature on a consent form along with the dated signature of the person conducting the consent discussion.

For prospective data collection, consent must be documented by the subject's dated signature or by the subject's legally acceptable representative's dated signature on a consent form along with the dated signature of the person conducting the consent discussion.

A copy of the signed and dated consent form should be given to the subject before participation in the study.

The initial informed consent form, any subsequent revised written informed consent form and any written information provided to the subject must receive the IRB/ERC's approval/favorable opinion in advance of use. The subject or his/her legally acceptable representative should be informed in a timely manner if new information becomes available that may be relevant to the subject's willingness to continue participation in the study. The communication of this information will be provided and documented via a revised consent form or addendum to the original consent form that captures the subject's dated signature or by the subject's legally acceptable representative's dated signature.

Specifics about a study and the study population will be added to the consent form template.

The informed consent will adhere to IRB/ERC requirements, applicable laws and regulations and Sponsor requirements.

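### Day-42 mortality drops patients of unknown status, and the death definition and consent wording can cause traced deaths to be lost

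*Protocol*

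**What the plan says.** **Estimate.** Section 7.3.2.1 of the protocol sets the rule: "Patients with missing or 'unable to determine' dead or alive status through Day 42 will be excluded". Both mortality formulas in 7.8.1 restrict the denominator accordingly, to patients "included in the study with dead or alive status reported x 100"%. Section 7.10 repeats the exclusion, and the consequence it draws is a smaller sample than estimated.

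**Death.** Section 7.3.2.1 says: "Death is defined as a patient with death is recorded in the medical history or death certificate can be provided through Day 42". It then points to 7.4 for data sources. Section 7.4 requires follow-up of retrospective patients whose chart does not show vital status, and says: "Death certificate information or the follow-up contact/report/record by investigator would be the data sources". The abstract names only death certificates for these patients.

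**Consent.** Sections 7.2.2 and 7.2.3 share an exclusion criterion: "Unable to provide written informed consent if Ethics review committee (ERC) requires". Section 8.1 accepts the subject's signature "or by the subject's legally acceptable representative's dated signature on a consent form". Section 7.4.1 adds, for retrospective data: "if a follow up is need for patients to collect dead or alive status through Day 42, the informed consent should be obtained".

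**Acknowledged bias.** Section 7.10 says that "survivor cases from retrospective data collection are easier to be reached to sign the ICF in the recruitment period". It names survivor bias, plans contact with relatives, and says that mortality could be underestimated or overestimated.

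**The concern.** A complete-case proportion is unbiased only if mortality among the excluded patients equals mortality in the whole cohort. The protocol itself doubts this.

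The planned safeguard is contact with relatives. It works only if a relative's report of a death counts as a death, and if someone other than the deceased patient can give the consent that tracing needs. Read literally, the definition in 7.3.2.1 does not secure the first condition, and the exclusion criterion and 7.4.1 do not secure the second. A telephone call could then establish survival, while a death reported without a certificate might be left as undetermined and excluded. Sites could code the same case differently.

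At stake is the headline number of the study. It matters most in the retrospective stratum, which 7.8.1 reports separately.

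**Working it through.** **1. The plan's own precision figures.** Table 2 (Section 7.5) uses exact Clopper-Pearson 95% intervals. All ten rows reproduce to 0.1 point. For example, 9/30 gives 14.7% to 49.4% (half-width 17.3), 15/30 gives 31.3% to 68.7% (18.7), and 6/40 gives 5.7% to 29.8% (12.1). These figures cover sampling error only.

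**2. What unknown status adds.** Let N be the number enrolled, u the unknowns and d the deaths among those known.

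- Complete-case estimate: d/(N − u)
- All unknowns alive: d/N
- All unknowns dead: (d + u)/N

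N follows the 30-40 in Section 7.5, and mortality of about 30% lies within the 15%-50% range used there. The number unknown is an assumption, because the protocol gives none.

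| N | u | Complete case | Exact 95% CI | All alive | All dead |
|---|---|---|---|---|---|
| 30 | 3 | 8/27 = 29.6% | 13.8-50.2% | 8/30 = 26.7% | 11/30 = 36.7% |
| 30 | 6 | 7/24 = 29.2% | 12.6-51.1% | 7/30 = 23.3% | 13/30 = 43.3% |
| 30 | 9 | 6/21 = 28.6% | 11.3-52.2% | 6/30 = 20.0% | 15/30 = 50.0% |
| 40 | 8 | 10/32 = 31.3% | 16.1-50.0% | 10/40 = 25.0% | 18/40 = 45.0% |

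In the second row, the lower exact limit for 7/30 is 9.9% and the upper limit for 13/30 is 62.6%. With both sources of uncertainty the range is 9.9% to 62.6%, against 12.6% to 51.1% for the complete-case interval alone.

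**3. Direction.** Suppose the chart already shows D deaths and A survivors, and d deaths and a survivors need tracing, with success rates r_d and r_s. Then

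observed = (D + r_d·d) / (D + A + r_d·d + r_s·a).

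Take 30 patients with true mortality 9/30 = 30%. The splits and the rates are assumptions.

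| Known (dead, alive) | To trace (dead, alive) | r_s = 0.9, r_d = 0.2 | r_s = 0.5, r_d = 0.2 |
|---|---|---|---|
| 7, 13 | 2, 8 | 7.4/27.6 = 26.8% | 7.4/24.4 = 30.3% |
| 5, 5 | 4, 16 | 5.8/25.2 = 23.0% | 5.8/18.8 = 30.9% |
| 3, 7 | 6, 14 | 4.2/23.8 = 17.6% | 4.2/18.2 = 23.1% |

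The estimate falls only when mortality among the excluded exceeds that of the whole cohort. In the first row it is 1.6/(1.6 + 0.8) = 66.7% with r_s = 0.9, but 1.6/(1.6 + 4.0) = 28.6% with r_s = 0.5. Poorer tracing of deaths usually pulls the estimate down, but it does not have to.

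**The case against.** Several parts of the protocol limit the problem.

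- Deaths recorded in the chart need no tracing.
- The consent exclusion applies only if the ethics committee requires consent. The committee may waive it for retrospective data, and 8.1 lets a representative sign where it does not. Section 8.1 can be read as explaining how the consent in the criterion is documented.
- Section 7.3.2.1 cross-refers to 7.4, so the strict reading of the death definition is one reading and not a stated rule.
- Section 7.10 discloses survivor bias and plans contact with relatives. It also gives an example in the opposite direction: less severe cases may have sparser records, so likely survivors may be under-represented.
- The primary analysis is stratified by prospective and retrospective collection.
- The SAP is not shown and may already contain bounds.

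Most of this stands. A reader might infer that the rules make unknown status depend on having died, so that retrospective mortality is certain to be too low. The documents do not support that, for the reasons above and because the second table shows null or slightly upward results. A reader might also infer that the unknowns matter more than sampling error. In the illustration they do not: 23.3% to 43.3% lies inside the exact interval of 12.6% to 51.1%.

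Two replies remain. The cross-reference points to a wider list of sources without changing the definition of death, and nothing in 7.4.1 says who consents for a deceased patient. Stratification shows a difference between cohorts but cannot separate poor ascertainment from case mix. The optional merging of the two cohorts in 7.8.1 does not address unknown status either.

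**Conclusion.** The point holds in a limited form. The protocol fixes a complete-case primary estimate while conceding that missingness may depend on outcome. Its wording on death and on consent can also undercut the contact with relatives that it relies on. Underestimated mortality is the more plausible direction, but it is not certain.

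The size cannot be derived, because the protocol gives neither the share of patients who need tracing nor the success rates. With 30 enrolled and an assumed 6 unknown, the bounds span 20 points (43.3 − 23.3), in addition to sampling error. With an assumed 3 unknown they span 10 points. The mismatched definitions and consent wording are protocol text and should be reconciled there. The absence of bounds from the protocol is not itself an error, since they may be in the SAP.

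**What to change.** 1. In 7.3.2.1 and the abstract, count as a death any dated death within Day 42 that is confirmed by follow-up contact, including a relative's report recorded by the investigator. This matches 7.4.
2. Reword the exclusion in 7.2.2 and 7.2.3, and the tracing sentence in 7.4.1. A patient should be excluded only if the ethics committee requires consent, no waiver applies, and neither the patient nor a legally acceptable representative can give it. This also settles who signs for a deceased patient.
3. Keep the Day-42 proportion. Report the number of unknowns by cohort and treatment line, with bounds that count all unknowns as alive and all as dead.

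Replacing the proportion with a Kaplan-Meier estimate would not cure the problem, because censoring unknowns assumes that their missingness is unrelated to death.

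The cost is wording changes and one extra sensitivity analysis. The downside is that some deaths will be accepted without a certificate.
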